
Measurements and Procedures
	
Different methods across modules will be used to achieve the objectives of this project. These modules will include qualitative and quantitative data approaches in order to enable a triangulation of the overall project results. The following modules will be used in the cRCT and the overall project: (i) Module 1: A combined RANAS and wellbeing survey, (ii) Module 2: Structured handwashing observations, (iii) Module 3: Microbiological analysis of hand rinse samples, (iv) Module 4: Diary approach for pre-defined health outcomes and absenteeism incidence, (v) Module 5: personal, physical, and social contextual factor survey, (vi) Module 6:FGDs and (vii) Module 7: Key informant interviews (KII).
 
Endpoints of Modules 1-3 will be assessed at baseline, at follow-up and endline of the cRCT. Module 4 will be used to collect data longitudinally over the course of 12 months. Module 5 will be assessed at baseline and only in Palestine, Module 6 and 7 will be used in the middle of the intervention phase in the intervention groups.

Number of Participants with Rationale (if no Power Analysis conducted)
	
The sample size calculation yielded that 13 schools are needed per arm with 50 students per school. With political instability and other factors which might lead to a loss of follow-up, we have 7 schools as backup schools. This will lead to 26 schools in total with a total number of 1300 students. The number of students participating in different modules will differ due to the capacity limitation of assessing the 50 students included in each school. For module 1, only 25 students of the 50 students included in the study in each school. For module 2, the 50 students included in the study in each school will be targeted for assessment using this module. For Module 3, 12 students out of the 25 randomly selected students to be targeted with RANAS and well-being survey will be targeted for assessment using this module.

	
Module 4 follows the sample size calculation of the cRCT design, hence 50 students from each of the 26 schools will be monitored. For Module 5, all students in the included classes in each school in Palestine will be delivered a survey to be self-reported by their parents. For Module 6, 10 FGDs (including students) and 5 FGDs (including teachers) will be administered and for Module 7, 10-20 interviews.

Study Duration	14 months

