If the opportunity for handwashing before eating was not possible for all students, an alternative scenario is proposed. In the class before the break, students will be engaged for 30 minutes in painting activity. At the end of the activity and as a reward, students will be provided with a popcorn snack and will be given free time of 15 minutes so they can eat together the snack. They need to use their hands for eating the popcorn, so, they are expected to wash their hands before eating it. They will also be told they can go outside the classroom if they want so they would be left with the choice to wash their hands before eating if they want. During that time, one observer will be standing close to the handwashing stations (or water points before installing the Grav't'eau) and recording all the students who take the

opportunity and wash their hands before eating and any other handwashing opportunity, e.g. after using the toilet. The observation will continue during the break time (45 minutes) so as to cover all opportunities for handwashing before eating for students who opted not to eat the snack and want to have lunch during the break. Students will be asked to keep the badges until the end of the activity. Other handwashing opportunities will be also recorded.

Also, if it was feasible the steps of handwashing will be observed for the students who wash their hands.

Consent for observation will be obtained at a school level, from the principal of the school, as well as from the parents.

Module 3: Microbiological analysis of hand rinse samples: Hand rinse samples of students will be collected after administering the survey with a modified glove juice method as described by Pickering *et al.* 2010. First, the enumerators will visually assess the cleanliness of the participant's hands with an observation form prompting for visible dirt in different areas of the hands, such as the thumb and under the fingernails (Contzen *et al.* 2015, Pickering *et al.* 2010 (b)).

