4.1 Primary endpoint

The main aim of the intervention is to improve hand hygiene. So, hand hygiene will be assessed in this study by assessing the occurrence, frequency and technique of handwashing behaviour using different tools. We will operationalise our target behaviour in this study as handwashing with water and soap at two critical events: (i) after using the toilet and (ii) before eating. However, the primary outcome in this study is the occurrence of handwashing with water and soap before eating during 3-hours observation for one day. It is selected as the primary outcome since it could be objectively assessed for all included students during the break whether because they have the opportunity since they eat their brunch during the break, or because they will eat a snack provided to them on the day of data collection.

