6.2 Determination of sample size

The number of clusters (schools) and students per school was assessed by simulations using the software R aiming for a power of 80% at the 95% confidence level. The Intraclass Correlation Coefficient (ICC) was assumed at 0.2. The simulation assumed a prevalence of handwashing occurrence before eating during the time of observation (3 hours) taking place over one day of 20% in control vs 45% in intervention schools after 1 year from the baseline. Based on this assumption, 13 schools are needed per arm with 50 students per school. However, the number of students assessed for different modules will differ due to the capacity limitation of assessing the 50 students included in each school.

For Module 1, only 25 students randomly selected out of the 50 students randomly selected from the classes included in the intervention in each school will be targeted. For Modules 2 and 4 the 50

students randomly selected from the one or two classes included in the intervention in each school will be targeted. For Module 3 only 12 students randomly selected out of the 25 students involved in module 1 in each school will be targeted. For Module 5, all students in the the classes included in the intervention in each school will be invited to participate by delivering a survey to be reported by one of their parents. For Module 6, 10 gender-separated FGDs will take place in the included schools in the intervention arm; 5 FGDs for each gender. In addition, 5 FGDs targeting teachers will be conducted. For Module 7, 10-20 interviews will be conducted.

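### Where the popcorn fallback is used, the painting session just before it may give pupils a study-made reason to wash that can be scored as the primary outcome

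*Combined protocol and SAP*

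**What the plan says.** Section 4.1 defines the primary outcome as whether a pupil washes with water and soap before eating during a three-hour observation on one day. The default setting, in Section 4 under Module 2, is the first school break, when local teams confirm that all pupils eat.

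Module 2 also proposes an alternative if that opportunity is not possible for all pupils. It starts with an activity: "In the class before the break, students will be engaged for 30 minutes in painting activity". Pupils then receive popcorn and 15 minutes of free time. The only reason given for expecting them to wash is that popcorn is eaten by hand. One observer stands near the water point, "recording all the students who take the" chance to wash before eating, and notes other handwashing occasions as well. Observation then continues through the 45-minute break.

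Each critical event is recorded as a yes or no. The extra response options cover poor visibility and missing soap or water, not the reason for washing. Section 4.1 accepts snack-day data as the primary endpoint on the same footing as the brunch break: pupils have the opportunity because of brunch "or because they will eat a snack provided to them on the day of data collection".

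The primary model (Synopsis, Statistical Analysis; Section 6.3) contains the intervention and a school random effect only. The Synopsis specifies the endline outcome.

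**The concern.** The snack is there to create an occasion for washing before eating. The painting has no stated measurement purpose, yet it comes directly before the minutes in which the outcome is scored. If it leaves paint on the hands, pupils have a second reason to wash, one the study created. An observer at the water point cannot see why a pupil washes, or whether the pupil then eats. No coding rule assigns paint removal to the other handwashing occasions, and the primary model has no term for the observation setting.

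Two consequences are possible. If paint-prompted washing is similar in both arms, both rates rise and the difference shrinks. If it is more common where soap and water are available, the difference can grow. The second pattern is plausible, because the control arm receives nothing for 12 months (Section 4), while intervention schools receive handwashing stations in Nigeria or rehabilitated facilities with soap dispensers in Palestine (Sections 2.3 and 2.3.2).

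**Working it through.** **1. Inputs from Section 6.2.** The calculation was done "aiming for a power of 80% at the 95% confidence level". On clustering: "The Intraclass Correlation Coefficient (ICC) was assumed at 0.2". Outcome rates: "20% in control vs 45% in intervention schools after 1 year from the baseline". Result: "13 schools are needed per arm with 50 students per school".

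**2. The plan's own figure.** Design effect = 1 + (50 − 1) × 0.2 = 10.8. For 13 schools of 50 per arm, the variance of the difference is (0.20 × 0.80 + 0.45 × 0.55) × 10.8 / (13 × 50) = 0.4075 × 10.8 / 650 = 0.00677, so the standard error is 0.0823. The noncentrality is 0.25 / 0.0823 = 3.04 on 24 degrees of freedom, and two-sided 5% power is 83.0%. Twelve schools give 79.7%. A beta-binomial simulation with a school-level t-test (20,000 runs) gives 81.8% for 13 schools and 78.1% for 12. Thirteen per arm is reproduced. Nothing in this point alters the sample size.

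**3. Assumptions that the documents do not supply.** Let w be the share of pupils who would not otherwise wash before eating, but have soap and water within reach, and wash off paint with soap. Let A be the percentage of pupils in an arm with that access, and p the planned rate. Pupils who already wash with soap must have access, so non-washers with access number A − p, and

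observed rate = p + w × (A − p).

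All values of w and A below are illustrative.

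**4. Full access in both arms (A = 100).** With w = 0.3:

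- Control: 20 + 0.3 × 80 = 44%
- Intervention: 45 + 0.3 × 55 = 61.5%
- Difference: 17.5 points instead of 25

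Range over w, with 13 schools per arm and ICC 0.2:

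| w | Control | Intervention | Difference (points) | Power |
|---|---|---|---|---|
| 0 | 20% | 45% | 25 | 83% |
| 0.1 | 28% | 50.5% | 22.5 | 70% |
| 0.3 | 44% | 61.5% | 17.5 | 47% |
| 0.5 | 60% | 72.5% | 12.5 | 29% |

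The table assumes that every school uses the fallback at endline. If only half the schools in each arm use it, w = 0.3 gives 20 + 0.5 × 24 = 32% and 45 + 0.5 × 16.5 = 53.25%, a difference of 21.25 points.

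**5. Unequal access (A = 40 control, 95 intervention).** With w = 0.3:

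- Control: 20 + 0.3 × (40 − 20) = 26%
- Intervention: 45 + 0.3 × (95 − 45) = 60%
- Difference: 34 points instead of 25

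**6. What decides the direction.** With the same w in both arms, the change in the difference is w × [(A intervention − A control) − 25]. Step 4 gives 0.3 × (0 − 25) = −7.5 points and step 5 gives 0.3 × (55 − 25) = +9 points. Painting inflates the difference if the access gap exceeds 25 points and shrinks it if the gap is smaller. The documents give no access figures by arm, so the sign cannot be settled from them.

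**The case against.** The strongest reply is that the endpoint does not depend on motive. A soap wash between painting and popcorn is, literally, a soap wash before eating. A reader might infer that the fallback outcome no longer measures the target behaviour at all. The documents do not support that: pupils who wash because they are about to eat are still counted, and painting at most adds others to them.

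The procedure is also conditional. The brunch break is the default, Section 9.6 provides the snack only if it is found to be needed, and Module 2 and Section 4.5 provide for piloting and adaptation. Nothing shows that painting will be used in any school. A reader might also take every round to be affected, but the primary analysis described in the Synopsis uses endline data without baseline adjustment. Painting at baseline or three months would not enter it.

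A further tempting reading is that any arm difference due to better access is bias. It is not. The primary objective (Section 3.1.2) concerns the whole multi-component package, and infrastructure and soap are part of it. Only the extra washing prompted by paint is a distortion.

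Finally, the documents say neither what paint is used nor that hands get dirty, and motive is unobserved at the brunch break too. The option for missing soap or water would help in examining access. These replies limit the scope and size of the point. They do not remove it: the brunch break contains no study-made soiling, and no rule keeps a paint-removing wash out of the primary count.

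**Conclusion.** The concern holds in a limited form. Where the fallback is used at endline, painting may contaminate the primary outcome with washing unrelated to eating, and neither the record nor the primary model can separate the two.

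The size and direction are unknown. Under an assumed 30% paint-washing rate among non-washers with access, and with the fallback in all schools, the planned 25-point difference becomes 17.5 points with full access in both arms, or 34 points with access for 40% and 95%. These figures show that the effect need not be negligible; they do not predict it. The result rests on painting actually soiling hands, on pupils using soap to clean them, and on the fallback being used at endline. If any of these fails, the distortion is absent. It is still worth correcting because the cue serves no stated purpose and is easily removed.

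**What to change.** In the Module 2 fallback, replace painting with an activity of the same length that does not soil the hands, for example a story or a quiz. Leave the snack, the free time and the observation procedure unchanged.

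If painting has already been used at endline, flag those schools and add a sensitivity analysis of the primary outcome without them. Dropping whole schools lowers precision: on the calculation above, power falls from 83.0% with 13 schools per arm to 79.7% with 12 and 75.8% with 11. If fallback use differs between arms, the remaining schools are also no longer a fully randomised comparison. The analysis should therefore support the primary result, not replace it.

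The cost is a small change to the procedure, with no added visits or staff and no effect on the sample size. The downside is possible non-comparability with any earlier round in which painting was used, which should be noted when rounds are compared.

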4.1 Primary endpoint

The main aim of the intervention is to improve hand hygiene. So, hand hygiene will be assessed in this study by assessing the occurrence, frequency and technique of handwashing behaviour using different tools. We will operationalise our target behaviour in this study as handwashing with water and soap at two critical events: (i) after using the toilet and (ii) before eating. However, the primary outcome in this study is the occurrence of handwashing with water and soap before eating during 3-hours observation for one day. It is selected as the primary outcome since it could be objectively assessed for all included students during the break whether because they have the opportunity since they eat their brunch during the break, or because they will eat a snack provided to them on the day of data collection.

4.2 Secondary endpoints

The most important secondary endpoints are:

- A) Good handwashing practice defined as students who wash their hands with water and soap after using the toilet assessed by structured handwashing observation
- B) Self-reported handwashing practice at the two critical events (before eating and after using the toilet) including occurrence, frequency and technique of handwashing behaviour will be assessed using the survey on a Likert scale ranging from almost never to almost always.
- C) The well-being of the students will be assessed using the KINDL tool (Ravens-Sieberer and Bullinger 1998).
- D) The log-transformed number of total coliforms and E.coli CFUs per hand before handwashing.
- E) Hygiene-related health outcomes and absenteeism. The health outcomes will be reassessed with local experts to assure feasibility before the start of the intervention.

Covariates are assessed with RANAS variables as exposure variables and good handwashing practice as outcome variable. Covariates for estimating the total effect of RANAS on good

handwashing practice are age, education, sex, socio-economic status, handwashing practices, and the water infrastructure of the schools.

4.3 Measures to minimize bias

Different biases might arise in this project. To prevent selection bias and confounding in the two study arms, we will use stratified block randomization to balance the two arms with respect to important baseline characteristics. Due to the nature of the intervention, neither the participants, nor the data collectors of the study, nor the statistician can be blinded. However, to reduce selective counting of CFUs on the hand-rinse samples, the lab workers assessing the number of CFUs will be blinded.

In Module 1, the RANAS and well-being survey, we expect a recall bias and a desirability bias. To minimize the recall bias, participants will not be asked to report any events which have taken place longer than a week ago. To reduce the desirability bias, the people administering the survey will not label themselves clearly as Tdh or Cesvi staff members, because local people know that Tdh and Cesvi often delivers humanitarian aid in the region and might want to impress the Tdh and Cesvi teams. Additionally, to reduce any study personnel bias, the data collectors will all receive a training in advance. Their ID will be recorded in the survey form in order to be able to conduct quality control.

For Modules 1 to 3, data collectors have to upload the completed surveys every night, once they have a stable internet connection. All of the surveys will have the data collector's ID. The PhD student from Swiss TPH will control every second day how long the data collectors took to complete a survey, if certain answers are always the same for specific data collectors and the amount of missing data per survey. In addition, the GPS location of the tablet will be recorded to make sure that the data collection actually took place at the predefined location. These components will be correlated in the statistical software R (version 4.1.3) to test for significant differences between data collectors. In case a data collector delivers significantly different results which are not deemed realistic by the Swiss TPH study team and the local main correspondents of Tdh and Cesvi, the staff will be asked to comply with predefined rules once. If they still do not comply afterwards, they will be replaced. Faulty data from these staff members can then not be used any more for analysing the results of the H4H project. Modules 1-3 will be repeated three months after the intervention and nine months after the intervention.

For Module 2, the handwashing observations, a Hawthorne effect is to be expected (the tendency of individuals to modify their behaviour due to their awareness they are being observed (McCambridge *et al.* 2014)). To minimise the Hawthorne effect, students will not be informed of being observed and the data collector will not get closer to the student being observed than needed to observe soap use. However, there is a possible source of bias resulting from the possibility of children connecting having someone close to the handwashing station with the intervention.

In Module 3, the microbiological analysis, a study personnel bias could influence the quality of the hand rinse samples and the accuracy of counting the CFUs. To be aware of differences between the data collectors, their ID will be stored during the sample collection on ODK. The number of CFUs per plate will be correlated with the people who collected the data to see if there are any significant differences between data collectors. The people counting the number of CFUs will be blinded and therefore do not know if the sample comes from the intervention or the control group. Additionally, every 10th sample will be duplicated during the data collection and the CFUs on every 10th plate will need to be counted additionally by another staff member as quality control.

To enhance the reliability of the outcomes from modules (1-3), it is proposed that each school be visited by two teams over two consecutive days for data collection. The first team of observers will conduct observations and collect hand rinse samples, while the second team of

interviewers will visit the same school on the following day to administer the RANAS and well-being survey to the students (as shown in Figure 3). This approach is recommended to avoid any potential positive impact on handwashing behaviour that may result from survey questions if students were surveyed first. Additionally, it will ensure that students' responses to the survey are not influenced as they will not be aware of being observed on the first day.

[figure not shown]

Figure 3: Flow-chart of data collection activities at baseline, follow-up and endline of the project depicting observations, the RANAS questionnaire and the hand-rinse samples.

In Module 4, students' hygiene-related health outcomes and absenteeism will be reported by one of the teachers in each school. To facilitate the process, a system of automatic weekly messages will be generated to remind teachers of filling out the absenteeism survey, and one of the tdh and Cesvi staff will follow and check their submissions on the ODK centre. However, different biases might arise. Depending on how dutifully the teachers report and on the severity of the health outcomes, a detection bias might occur. We will test for this bias by correlating the school with the proportion of reported days of absenteeism and health outcomes over a year. In order to intervene in case such differences exist, we will correlate the data in each quarter of the study year as a form of quality control. In addition, a form of selection bias can happen if a certain group of students falsely report a medical reason as an excuse for their absence on certain days. For example, a student might report his/her reason for being absent is being sick with any of the predefined hygiene-related health outcomes. To minimise such biases, the form of absenteeism that the teachers use contains a question about the availability of a medical report. If there is no medical report and the teacher still questions the reliability of the reason for the absence, they are asked to depend on their experience and knowledge to judge if the student's excuse is false or not. We are aware that this module is suboptimal due to the difficulty to confirm the reasons for the students' absenteeism. However, this is only part of an exploratory objective. We still think that if differences can be observed between the two intervention arms, this module is of high importance as it would demonstrate the significance of the H4H MCI in schools. If these differences can be demonstrated on a local level, motivating local schools and the Ministry of Education for future handwashing interventions might become easier.

To assure the quality and functioning of the Gravit'eau handwashing stations, regular integrity tests and water quality tests will show if the systems are still functional and capable to remove the bacteria. *E.coli* tests of handwashing water will show if there is any recontamination or any integrity problem. In case there is a problem, we will provide an alternative solution (e.g. bucket with soap) and rehabilitate the handwashing systems or dose chlorine into handwashing systems and repeat the test.

In case a school has 25% higher negative health outcomes than the average of all schools, the regional Ministry of Education and Ministry of Health will be consulted to check if this is usual. If not, the study will have to be stopped in this school.

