Study Schedule	
For Nigeria: May 2023 of First-Participant-In July 2024 of Last-Participant-Out
 
For Palestine: March 2023 of First-Participant-In May 2024 of Last-Participant-Out

Investigator(s)	
[name]. [name] Swiss Tropical and Public Health Institute [name] [contact] [contact]
 
PhD candidate (research assistant) under supervision of [name]. [name]: [name] Swiss Tropical and Public Health Institute [name], Switzerland [contact]
 
[name] Terre des hommes Nigeria [name] [contact], [name] [contact]
 
[name] Project coordinator Cesvi Palestine [name] [name] [contact]
 
[name] Junior Programme Officer Skat Foundation [name] [contact] [contact]

Study Centre(s)	Nigeria and Palestine
Statistical Analysis incl. Power Analysis	The number of clusters (schools) and students per school were calculated using the software R with a power simulation of 80% developed by [name]. The Intraclass Correlation Coefficient (ICC) was assumed at 0.2. The simulation assumed a prevalence of handwashing occurrence before eating during the time of observation (3 hours) taking place over one day of 20% in control vs 45% in intervention schools after 1 year from the

	
baseline. Based on this assumption, 13 schools are needed per arm with 50 students per school.
 
The baseline data will be reported descriptively. The imbalance at baseline between trial arms will be assessed in terms of clinical importance rather than in terms of statistical significance. The intervention effect will be estimated with logistic mixed effect regression to adjust for potential correlation within schools. For the primary analysis, the model will include only the outcome (handwashing occurrence before eating during the time of observation (3 hours) taking place over one day and assessed at the endline) and the intervention as a predictor and school as a random effect. Further analyses will include known confounders and variables imbalanced at baseline. All analyses will use the available case population. No imputation of missing data will be done because loss to follow-up is usually small to moderate in school-based studies.

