4 STUDY DESIGN

The overall project will follow a multi-center cluster-randomized controlled trial (cRCT) design (Figure 2). Prior to this study, a group of schools in the study's target areas were surveyed by the Tdh (in Nigeria) and Cesvi (in Palestine) using the Facility Evaluation Tool for WASH in Schools ([FACET WINS](#)) which is a monitoring tool for WASH delivery services in schools. From these schools a subsample was identified which fulfils certain inclusion criteria (for the inclusion criteria see chapter 5.2 Inclusion criteria).

This subsample was handed over to the local Tdh and Cesvi collaborators who carefully assessed the security situation around the schools. The Tdh and Cesvi collaborators then selected 26 facilities per country, which are most probable to still be accessible for data collection within the next year. These 26 schools will then be allocated to the two arms (intervention vs. control) with covariate constrained stratified randomization using computer-generated randomization code provided by a statistician not involved in any field activities. The intervention arm will receive the full intervention package (handwashing station, behavioural change intervention, capacity development, and management support). The control arm will receive nothing for the duration of the intervention (12 months). Afterwards, they will receive the same intervention package with potential improvements identified in the former intervention group.

In the selected schools, 50 eligible students from each school will be selected from one or two classes within the age group (10-12 years) using random sampling. If the school has at least one class that has ≥ 50 students within the target age group, the sample will be selected from that class, otherwise, the sample can be selected from two classes. For module 1, only 25 students of the 50 students included in the study in each school will be involved. For module 2, the 50 students included in the study in each school will be targeted for assessment using this module. For Module 3, 12 students out of the 25 students targeted with assessment using module 1 will be targeted for assessment using this module.

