6.3 Description of statistical methods

Baseline characteristics will be summarized using descriptive statistics. The difference in the observed proportion of washing hands before eating between two study arms at follow-up will be investigated using logistic mixed effect regression to adjust for potential correlation within schools. In the primary analysis only the intervention will be included as predictor and school as a random effect.

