6.3.1.2 Secondary Analyses

In a secondary analysis the models will be adjusted for known confounder and additional predictors imbalanced at baseline.

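### Section 4.3 rules out blinding the statistician for a reason that applies only to pupils and data collectors; a masked analysis is feasible and would protect the few choices still open

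*Combined protocol and SAP*

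**What the plan says.** Section 4.3 (Measures to minimize bias) says that "neither the participants, nor the data collectors of the study, nor the statistician can be blinded" and attributes this to the nature of the intervention. It gives no reason specific to the statistician. The same section masks one group: "the lab workers assessing the number of CFUs will be blinded". Section 4 (Study design) has the allocation come from a "computer-generated randomization code provided by a statistician not involved in any field activities". The documents do not say whether that person also analyses the data.

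On the analysis, section 6.3 fixes the primary model: "In the primary analysis only the intervention will be included as predictor and school as a random effect". Section 6.3.1.2 adds: "In a secondary analysis the models will be adjusted for known confounder and additional predictors imbalanced at baseline". The Synopsis, under Statistical Analysis, says how imbalance is to be judged: "The imbalance at baseline between trial arms will be assessed in terms of clinical importance rather than in terms of statistical significance". No list of confounders for the intervention effect, no threshold for imbalance and no time for that judgement are given.

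Section 4, Module 2, makes the primary outcome dichotomous, but adds response options for a pupil who could not be seen and for soap or water that was missing. No rule maps these options to yes, no or missing. The documents describe no coded-arm dataset, no blind data review and no sign-off before arms are revealed.

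**The concern.** The reason given in section 4.3 does not reach the person it is applied to. Pupils use the new facilities and observers stand beside them, so neither can be masked. An analyst receives records and can work with arms labelled A and B.

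This matters because the observers of the primary outcome are necessarily unmasked, so the analysis is one of the few later stages where knowledge of the arm can still be withheld. If scoring rules, exclusions or adjustment covariates are settled by someone who can see which arm each choice favours, the choices can lean towards one arm without anyone intending it. A declaration that masking is impossible also closes off a safeguard that the project could use.

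**Working it through.** **1. Does the stated reason apply?** Section 4.3's reason is the nature of the intervention. Section 2.3 describes that intervention as stations, rehabilitated infrastructure, behaviour-change activities, training and management support. All of these are visible at the school. None is visible in a data file unless a variable reveals it.

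**2. What is fixed and what is open?**

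| Decision | Status in the documents | Reaches the primary result? |
|---|---|---|
| Primary model | Fixed (section 6.3; Synopsis) | Not open |
| Scoring of the extra observation options | No rule (section 4, Module 2) | Yes |
| Exclusions at analysis | Available cases, intention to treat (section 6.3.1); a collector's faulty data may be dropped (section 4.3) | Yes |
| Adjustment covariates | Unlisted (section 6.3.1.2; Synopsis) | No, secondary analysis only |

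The covariate list in section 4.2 concerns RANAS factors as exposures, so it does not fill the last row. Section 6.3 places the comparison at follow-up and the Synopsis at endline. Section 6.2 (one year after baseline) agrees with the Synopsis, so I treat this as wording to reconcile and not as an open choice.

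**3. How much could the scoring matter?** The documents give no frequency for the extra options, so this is an illustration on assumptions. Take the planned rates in section 6.2: 20% control, 45% intervention. Assume the 20% counts pupils without soap or water as non-washers, that they make up a fraction *f* of control observations, and that there are none in the intervention arm. Scoring them as missing instead gives a control rate of 0.20 / (1 − *f*):

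- *f* = 0: 20.0%, difference 45 − 20 = 25 points
- *f* = 10%: 0.20 / 0.90 = 22.2%, difference 22.8 points
- *f* = 20%: 0.20 / 0.80 = 25.0%, difference 20 points

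Over this assumed range the scoring rule moves the contrast by 0 to 5 points. The option may well be commoner in control schools, because the intervention supplies the infrastructure.

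**4. Does masking change the sample size?** First, the plan's own figure. Inputs from section 6.2: 20% versus 45%, ICC 0.2, 50 pupils per school, 80% power, 95% confidence; two-sided, since section 6.1.1 tests for a difference.

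- Individuals per arm, with mean proportion 0.325: [1.96 × √(2 × 0.325 × 0.675) + 0.8416 × √(0.20 × 0.80 + 0.45 × 0.55)]² / 0.25² = (1.2983 + 0.5373)² / 0.0625 = 53.9, so 54
- Design effect: 1 + 49 × 0.2 = 10.8
- Schools per arm: 54 × 10.8 / 50 = 11.7, so 12; one more for the t distribution gives 13
- Power by noncentral t: 79.7% with 12 schools, 83.0% with 13

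The 13 per arm reproduces. Nothing in it depends on who knows the labels, so masking leaves it unchanged.

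**5. What would reveal the arm in the data?** Participant IDs carry school initials (section 9.4), the tablet's GPS position is recorded (section 4.3), and the Gravit'eau spot-check forms (section 7.1) concern stations installed as part of the intervention. Recoding the arm label alone would therefore not be enough.

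**The case against.** The strongest reply is that the gaps are ones of prespecification. A written scoring rule and a covariate list would close them whether or not anyone is masked. That largely stands: the rule and the list are needed in any case. Masking adds protection only for judgements that cannot all be foreseen.

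Other points also stand. The primary model is not open to choice. Implausible collector results are judged during data collection by the study team and the field partners' main correspondents, so masking the statistician would not mask that decision; only exclusions made at analysis are covered. Baseline imbalance could be judged before any endline outcome exists. Since no time is set, it is an inference, not something the documents state, that it would be judged with results in view. The laboratory comparison is loose, because counters see single plates and not school-level outcomes.

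A reader might infer that an unmasked statistician inflates the false-positive rate severely, and might support this by simulating an analyst who keeps the smallest p-value. With 26 school means, no true effect, five assumed covariates with coefficient 0.3 and all 26 models of up to three covariates, that search gives 15.0% false positives. It also gives 15.0% with the arm labels swapped, because a two-sided p-value does not depend on which arm is called A. Masking alone would remove none of it; the figure measures an unfixed covariate list. Nor does the plan select by p-value. Adjusting instead for every covariate whose arms differ by more than 0.25 or 0.5 SD (assumed thresholds) gives 3.4% and 3.8%, which is no inflation. The documents do not support the stronger reading.

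**Conclusion.** The concern holds in a limited form. Section 4.3 claims an impossibility that its reason does not establish, and it passes over a low-cost guard. The exposure is confined to the scoring of the extra observation options, exclusions made at analysis, and the covariates of the secondary adjusted analysis.

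No inflation of the type I error can be attributed to the lack of masking from what the documents give. The only size available is the illustrative shift of 0 to 5 percentage points in the planned contrast from the scoring rule, which rests on an assumed 0 to 20% of control observations in one category and none in the intervention arm. This is a worthwhile inexpensive improvement and not a threat to the validity of the primary model.

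**What to change.** - Remove the statistician from the list of people in section 4.3 who cannot be blinded.
- State that the analyst receives recoded school and arm labels (A/B), with school initials, GPS positions and Gravit'eau monitoring data withheld. The randomising statistician, or another person who does not analyse the data, holds the key.
- State that outcome coding, exclusions and adjustment covariates are signed off before unmasking. The covariates are preferably fixed from baseline data before endline data are collected.

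The cost is small but not nil: some recoding, and a key-holder separate from the analyst, which the documents do not yet provide for. Masking may be imperfect, because a large effect, or an uneven frequency of missing soap or water, could reveal the arms. That is a reason to complete the sign-off early, with the scoring rule written before arm-level tabulations are made. Sample size, schedule and field work do not change.
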